5.7 Withdrawal of Subjects

There are not any anticipated circumstances under which subjects will be withdrawn from the research without their consent. Veteran participants may withdraw from the study at any time by telephone or email, which will be documented in the study files by the PI. Veteran participants can also stop any of the surveys – and for the relevant sub-sample, the interviews – at any time while they are happening.

6.0 Reporting

[name] will lead regular study team meetings and will formally query the study team specifically for any serious adverse events, unanticipated occurrences related to subject safety, breaches of study protocol or confidentiality. Study team members will also be directed to bring any such problems to the attention of the PI as they occur. The PI will report relevant

occurrences both to the Central IRB and the site R&D Committee per VA procedures.

7.0 Privacy and Confidentiality

The study will not disclose protected health information. All information on individual subjects will be kept confidential on restricted server files behind the VA firewall. Collected data will be used only for research purposes and identifiers will be removed from all data files, which will only be identified with a study identifier (except for audio recordings which include voice as an identifier). Only study team members will have access to the secure file containing study data on encrypted VA served, and access will be removed for personnel when they are no longer part of the study through IT request. Study staff will be well trained to protect the privacy of study participants and prevent breaches of confidentiality. All study team personnel with access to sensitive patient data will stay current on required VA information security and privacy policy trainings. Reported results will not contain any individual identifiers. Research records will be destroyed in accordance with the VHA Records Control Schedule (RCS). Paper files will be shredded. Research data maintained on electronic storage and memory devices such as computers, laptops, and CDs will be destroyed in a way they cannot be retrieved.

8.0 Communication Plan

All site approvals will be obtained in compliance with Central IRB procedures. For each site participating in the study, we will notify the Director prior to conducting research at his/her facility. Also, we will process any changes in the protocol, informed consent, or cessation of engagement in research for any sites in concordance with Central IRB procedures.

The PI will meet regularly with the study team, with local site co-Investigators participating via VANTS conference lines and Skype videoconferencing systems.

Appendix A: Description of the Intervention and Randomization

Unmet Needs Screen:

Veterans (anticipated N=1760) will be screened for unmet needs (index screen) and those identified as having at least one unmet need (target N=880) will be randomized to one of three study arms and screened again 6-months later. We will use the sealed opaque envelope program to generate randomization. For the index screen, a study Research Assistant (RA) will administer the screening instrument to Veterans by phone prior to the Veteran's upcoming primary care (PC) clinic appointment to gather data on nine unmet needs (full screen in **Appendix I**). Six months after the index screen, the RA will re-screen each Veteran participant by phone. For each completed screen, we will provide Veterans \$15 for their time.

After the RA determines each participant is eligible (see Section 5.2. Recruitment Methods), randomization will occur by the RA opening sealed envelopes that reveal the treatment assignments (screening, awareness, or assistance). Envelopes will be opened for each participant in the order they are recruited. The RA will then inform the participant of their assignment.

Resource Sheets:

For Veterans in the Awareness and Assistance arms, the RA will provide (via U.S mail) Resource Sheets tailored to the unmet needs identified in the index screen. During the index screen (by phone), the RA will inform the Veteran that they will receive a Resource Sheet in the mail and mail the Resource Sheets to the Veteran within two days of the index screen. During the index screen, the RA will additionally ask the Veteran if they would also like to receive the Resource Sheets via email. For Veterans who respond affirmatively, the RA will send the Resource Sheets as an email attachment during the index screen phone call and offer to review its content with them. The email message will be sent via encrypted email and will not solicit reply. (**Appendix G** contains the phone script for this interaction, and **Appendix P** contains the Resource Sheet email text and the cover letter for mailing.)

For each of the nine unmet needs, following the approach used in the VISN 1 pilot and at our academic affiliate hospital (Boston Medical Center), a Resource Sheet will include the names of available resources within VA and/or the local community that can help address the identified need(s) and contact information (e.g., address, phone, website, email) and hours of operation. (See **Appendix O**

for sample Resource Sheets currently used in VISN 1 unmet need screening and referral pilot).

Prior to study initiation, we will contact all organizations listed on the Resource Sheets to determine if they have current capacity for referrals generated from our study. Organizations without such capacity will be replaced with other organizations with capacity. Then, following practices for regular updating of resource information used by our colleagues and by national organizations addressing unmet needs (e.g., Health Leads, NowPow), RAs at each site and in consultation with local SW services will contact the programs listed on the Resource Sheets monthly, to update status for accepting referrals and contact information. RAs will track and record time spent maintaining the Resource Sheets to identify the resource demands of this component of the intervention for replication purposes.

Social Work-Supported Referrals

In the Assistance arm, we will hire and train social workers (one per site) to support Veterans to connect with resources following a standard operating procedure informed by current VA SW practices. Following the index screen and provision of tailored Resource Sheets, the RA will offer and encourage Veterans in this arm to receive assistance from a SW. Veterans may choose to opt out, but if they assent, the RA will provide the Veteran with the name and phone number of the SW who will contact the Veteran within two business days of the index screen (making up to five attempts to reach the Veteran by phone). During this initial call, the SW will use a standardized bio-psychosocial assessment tool used by VA SW and proven motivational interviewing methods^{20, 21} to uncover details of the Veteran's unmet needs, identify barriers to resolving the unmet needs, and develop an action plan for the Veteran including how to overcome the identified barriers. In addition, following VA SW practice, the SW will call the resource(s) to which the Veteran has been referred to inform them the Veteran will be coming for services. The SW will conduct initial follow-up by phone one week after the interview/action plan development, with planned subsequent phone outreach every two weeks for up to seven weeks. At each call and as needed (i.e., if Veteran has not yet connected to services), the SW will again employ motivational interviewing methods with the goal of re-affirming the action plan or modifying it as needed. The SW will track and record all Veteran encounters in a research data base, including time spent, challenges and best practices identified.

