5.5 Study Evaluations

RCT participants will be asked to complete three brief surveys over a 6-month period. A small sub-set of participants will additionally be invited to participate in qualitative interviews.

Index Unmet Need Screen (survey #1): We will assess unmet needs among trial participants based on the index screen (administered prior to randomization). See **Appendix I** for the Index Unmet Need Survey.

Eight-Week Follow-Up Survey (survey #2): Eight weeks after the index screen, the RA will conduct phone follow-up with each Veteran to assess if they connected to any new resources in the intervening time and if so, to which one(s). See **Appendix J** for the Eight-Week Follow-Up Survey and accompanying phone script.

6-Month Unmet Need Re-Screen (survey #3): Six months after the index screen and by phone, the RA will re-administer the unmet need survey modified slightly

to exclude questions related to preferences for assistance (see **Appendix K** for the Six-Month Unmet Need Survey and accompanying phone script). We will define unmet need reduction in two ways: 1) one or more of baseline unmet needs no longer identified as an unmet need at the 6-month re-screen; and 2) percentage of baseline needs not reported as unmet needs at 6-month rescreen.

Qualitative Interviews with Veterans: Among study participants, we will purposefully select and recruit 60 Veterans to participate in qualitative interviews. The interviews are designed to understand the conditions that facilitate or impede a Veteran connecting to resources, as well as the conditions under which resources do or do not address a Veteran's needs. The RA at each study site will conduct the interviews. See **Appendix L and M** for the Veteran Interview Guides and accompanying phone scripts).

Qualitative Interviews with Representatives of VA and Community Resources: To understand how VA- and community-based programs experience the intervention, we will interview a purposeful sample of the VA- and community-based programs that trial participants used as a result of the intervention. The RA at each study site will conduct the interviews. See **Appendix N** for the Resource Representative Interview Guide and accompanying phone script.

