7a. Do you have any questions (*RESPOND TO ANY QUESTIONS ASKED*).

Thank so much you for your time (*END CALL*).

8. Among Participants who identified one or more needs, randomize to one of three study arms.

9. Among participants randomized to Arm 1 (Screening): Thank you for completing Part One of the study. You are eligible for Part Two of the study and have been randomized to Group A. This means that in 8 weeks, I will recontact you to ask a few more questions about your needs. Do you have any questions? (*RESPOND TO ANY QUESTIONS ASKED*) (*MENTION GIFT CARD AND VERIFY MAILING ADDRESS**.) Thank you for your time.

**(CIRB Note: local sites will explain their payment process, which differs from the prime site)*

10. Among participants randomized to Arm 2 (Awareness): Thank you for completing Part One of the study. You are eligible for Part Two of the study and have been randomized to Group B. I would like to provide you with some written material about programs and agencies that might be able to help you with the needs you identified. I will mail you this material within the next two business days. If you like, I can also email the material to you right now and we can review it together over the phone. Would you like to do that?

If Yes to email: Great, I can email that to you right now. (CONFIRM/ASK FOR PARTICIPANT'S EMAIL ADDRESS AND SEND ENCRYPTED EMAIL.)

If No to email: No problem. You can look for a written list of resources in the mail in the next several days. The information will include my phone number in case you have any questions about the information once you receive it.

10a. I will also be mailing you a \$15 gift card* to thank you for your time. And in 8 weeks, I will recontact you to ask a few more questions about your needs. Do you have any questions? (RESPOND TO ANY QUESTIONS ASKED) (VERIFY MAILING ADDRESS FOR GIFT CARD)* Thank you for your time.

[\(CIRB Note: local sites will explain their payment process, which differs from the prime site.\)](#)*

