Appendix J: Eight-Week Follow-Up Survey

Phone Contact:

Hello, my name is _____, I'm calling from the (Name of VAMC). I am trying to reach [Name of Veteran].

Not Present: I'll call back another time, thank you. Is there a good time to try calling back?

Voicemail: Hello, my name is [name of research team member], I am calling from the (Name of VAMC). I wanted to speak with [Name of Veteran] about the Resource Needs Study. It's time to complete one of the brief questionnaires that are part of this study, it will only take about 5 minutes to complete. Please contact me at [name]. If you get my voicemail please leave your name, the best number to reach you at, and the most convenient times to reach you. Thank you.

Present: Hello, my names is [name of research team member] and I work at the (Name of VAMC). I wanted to speak with you about the Resource Needs Study you are participating in. It's time to complete one of the brief questionnaires that are part of this study, it will only take about 5 minutes to complete. Do you have a few minutes now?

If No: When is a good time for you to answer some questions about your social circumstances? (*SCHEDULE A TIME AND CONFIRM BEST CONTACT NUMBER*)

If Yes: Great, let's get started.

Screening Survey

1. Since we last talked on [insert index screening date], were you able to connect with any new programs or services for help with [insert needs identified from index screen)?

Yes

No (skip to Q5)

2. Which programs or services did you connect with?

3. Were you able to get the help you wanted from this (these) program(s)?

Yes

No

4. How did you connect with this (these) program(s)?

Probes

phone call

walk in

web-based

e-mail

5. Why were you unable to connect with the [insert specific resources that were provided to respondent at index screen, e.g., food, employment] programs(s)?

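### The research assistant who reveals the arm and helps deliver it also records the self-reported primary outcome; an arm-blind caller at another site would remove the interviewer's share of the bias, but not the Veteran's

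*Combined protocol and SAP*

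**What the plan says.** Appendix A gives the RA a chain of tasks on the index call. The RA administers the screen, and then "randomization will occur by the RA opening sealed envelopes that reveal the treatment assignments". Next, "The RA will then inform the participant of their assignment". The RA mails the Resource Sheets in the Awareness and Assistance arms, and can email them and go through them on the phone. In Assistance, "the RA will offer and encourage Veterans in this arm to receive assistance from a SW".

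Outcome collection falls to the same role. Section 5.5 says that eight weeks later "the RA will conduct phone follow-up with each Veteran to assess if they connected to any new resources", and it also gives the six-month re-screen to the RA. The scripts indicate that the same person is meant. In Appendix G the RA tells a Veteran in the Screening arm: "This means that in 8 weeks, I will recontact you to ask a few more questions about your needs"; the wording for the other two arms is equivalent. Item 1 in Appendix J, which records the primary outcome, begins: "Since we last talked on [insert index screening date], were you able to connect with any new programs or services". Items 2 to 4 ask which programs, whether help was obtained, and how contact was made. Item 5 has a slot to "insert specific resources that were provided to respondent at index screen".

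Section 5.6 names connection at eight weeks as the primary outcome and predicts that Assistance will exceed Screening, with Awareness between them.

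**The concern.** The primary outcome is one self-reported answer, and the supplied text sets no operational threshold for connecting or for a resource being new. The caller therefore has room to probe and interpret. That caller knows the arm, helped deliver the intervention and, under Appendix A, keeps the site's Resource Sheets up to date, so knows which programs to suggest. The predicted ordering of the arms matches the ordering of contact and assistance, so interviewer bias would most plausibly favour the hypothesis.

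No independent check is described. The clinical record is used in section 5.6 only for social work use in the 12 months before the intervention, not to confirm reported connections. A larger sample does not help, because a fixed bias becomes easier to declare significant as the sample grows.

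**Working it through.** **Inputs from the documents.** Sections 5.1 and 5.6: 880 randomized within site (293 per arm); 50% retained at eight weeks, so 440 in total and 440/3 ≈ 147 per arm; two-sided alpha .05; 80% power at an adjusted odds ratio of 2.1, described as 15% more likely.

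**Assumptions.** No control-arm connection rate is given. Reading 15% as 15 percentage points and solving for an odds ratio of 2.1 gives two pairs of rates: 21.5% v 36.5%, or 63.5% v 78.5%. A 30% baseline is used as a third, purely assumed, value. The size of the reporting bias is also assumed.

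**1. The plan's own power figure.** Pairwise comparison of proportions, 147 per arm, no design effect because arms are randomized within site:
- pooled SE = √(2 × 0.29 × 0.71/147) = 0.0529
- unpooled SE = √((0.215 × 0.785 + 0.365 × 0.635)/147) = 0.0522
- power = Φ((0.15 − 1.96 × 0.0529)/0.0522) = Φ(0.886) = 81.2%

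The 63.5% v 78.5% pair gives the same value. The stated 80% reproduces and is not in dispute.

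**2. Error rate from biased recording alone.** Let both arms have true rate p, and let a fraction f of Assistance non-connectors be recorded as Yes. The recorded Assistance rate is q = p + f(1 − p), and the spurious difference is d = f(1 − p). With SE = √((p(1 − p) + q(1 − q))/147), the chance of a significant result is Φ(d/SE − 1.96) + Φ(−d/SE − 1.96).

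Worked example, p = 0.30 and f = 0.10: q = 0.37, d = 0.07, SE = 0.0549, d/SE = 1.275, giving Φ(−0.685) + Φ(−3.235) = 24.7%.

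| Baseline p | f | Recorded q | d (points) | Odds ratio | False-positive rate |
|---|---|---|---|---|---|
| 21.5% | 5% | 25.4% | 3.9 | 1.25 | 12% |
| 21.5% | 10% | 29.4% | 7.9 | 1.52 | 34% |
| 30% | 5% | 33.5% | 3.5 | 1.18 | 10% |
| 30% | 10% | 37.0% | 7.0 | 1.37 | 25% |
| 63.5% | 5% | 65.3% | 1.8 | 1.08 | 6% |
| 63.5% | 10% | 67.2% | 3.7 | 1.18 | 10% |

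**3. Effect of sample size.** A flat 5-point reporting difference (5/15 = one third of the design effect) gives 15% to 17% at 147 per arm. With no attrition, at 293 per arm, it gives 25% to 29%. The range in each case covers baselines of 63.5% and 21.5%.

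**4. Workload.** If sites recruit equally, there are 880/3 ≈ 293 eight-week calls per site whoever dials. At the script's five minutes each, that is 293 × 5/60 ≈ 24 hours of talk time per site if every Veteran is reached.

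**The case against.** The strongest objection is that the caller is not the main source of bias. Veterans are told their arm, all three arms are explained at consent (section 5.1, on protection from risk), and Assistance Veterans receive repeated social worker calls. A reader might infer that cross-site calling would blind the primary outcome, or remove the whole inflation in the table. The documents do not support either inference. The Veteran supplies the answer and knows the assignment, and the calculation does not separate the Veteran's share from the interviewer's. This part of the objection stands.

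Other points also limit the concern:
- Item 1 is worded identically in all arms, and RA contact differs only by part of one call eight weeks earlier. The large contact difference is with the social worker, who is not assigned the outcome call. What differs is mainly the caller's knowledge and stake, so a familiar-caller effect alone may be modest.
- A Yes leads to a request to name the program, which makes a careless Yes harder to sustain. It is not verification, however, and an RA who maintains the sheets can suggest a name.
- Item 5 comes after item 1. A reader might infer that its wording contaminates the primary answer, but it cannot alter an answer already given. Its own examples, food and employment, are names of needs. The remaining risk is that a pre-filled form shows the arm before the call begins.
- The table uses a pairwise z-test, whereas section 5.6 plans a hierarchical model across three arms. Nothing in the documents shows that 5% to 10% of non-connectors would be misrecorded.
- Payment processes, the on-call social worker and the crisis hand-off are tied to the site, so moving calls is not cost-free.

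None of this removes the overlap of roles, which is plain in Appendix A, section 5.5 and the scripts.

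**Conclusion.** The concern holds for the interviewer's part. As written, a caller who revealed the arm and helped deliver it records an unverified yes/no primary outcome, and the likely direction of bias favours the hypothesis. The false-positive rates, 6% to 34% across the baselines and bias sizes tried, illustrate sensitivity. They are not estimates of bias in this trial, and the proposed change would remove only an unknown part of the inflation. No separate magnitude has been worked out for the six-month call.

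Two limits come from the material available. The personnel section was not available, nor was the Data Analysis Plan that section 5.1 says was submitted for DSMB approval. So it cannot be concluded that assessor blinding is absent everywhere, only that the supplied text does not describe it. For the same reason, feasibility without new staff is an assumption. It rests on one RA per recruiting site (section 5.2), surveys all by phone (section 5.1), and a survey database open to all personnel who need it (section 5.1).

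The change is worth making. It leaves N, alpha and stated power untouched and reduces an avoidable bias in the primary comparison.

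**What to change.** Assign the eight-week call, and preferably the six-month call, to an RA at another recruiting site. A caller who learns the arm at eight weeks should not make that Veteran's six-month call. In detail:

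- Build a REDCap call form that shows the index date and index needs but hides the arm, the social worker log and the mailing records.
- Ask and lock items 1 to 4 first. Replace the item 5 insert with the name of the need, so that the pre-filled form cannot reveal the arm.
- Reword the opening of item 1 and the site greeting in Appendix J, both of which presume the original caller. Change the first-person promise of recontact in Appendix G.
- Ask Veterans at the start not to mention their group or a social worker, and have the caller record whether the arm became known.
- Keep payment, the on-call social worker and the crisis hand-off with the Veteran's own site.
- State in section 5.6 that only the caller is blinded and that participants' own reporting bias remains.

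The number of calls does not change. The costs are cross-site scheduling, database permissions, sharing contact data between sites, and possibly a slightly lower response from a less familiar caller. With 50% non-response already assumed at eight weeks, response should be monitored by arm. If follow-up has begun, the change can still apply to the remaining calls.

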Appendix B: Protocol for Warm Hand-Off to Veterans Crisis Line

Taken from the Quantitative Workstream Handbook

For those with “Higher” or “Indeterminate Higher” Risk:

→ Offer Veterans Crisis Line and warm hand-off (Refer to [VCL Warm Hand-off Instructions](#) Page (see last page)). Use the [contact] and DO NOT provide this number to Veterans.

- If the Veteran declines warm hand-off to VCL, attempt to keep the Veteran on the phone while also contacting the Veterans Crisis Line the VHA Suicide Prevention Office at [contact] .
- If the caller disconnects before the transfer can be made, send email to the VHA Suicide Prevention Office at the above email address.
- VCL will continue outreach attempts until the Veteran is reached or for one week, and will involve the Veteran's local Suicide Prevention Coordinator (SPC) as appropriate.

Interviewer Reads: *You mentioned earlier that you have had thoughts about harming yourself. [OR for those who refuse to answer question(s): You seem hesitant to answer questions about possible self-harm.] I want to encourage you to talk with your doctor or mental health provider about these thoughts, and I will send a message to the Suicide Prevention Coordinator at your VA Medical Center mentioning that you have expressed these concerns. They may contact you to discuss these concerns further. In addition, I can transfer you to someone at the Veterans Crisis Line so that you can talk further right now with someone who is qualified to help you in this situation.*

- *In the rare occurrence that the interviewer is concerned about imminent risk (i.e., caller has already hurt self/others or has immediate plan to harm self/others and has access to means to inflict harm), contact Veterans Crisis Line (VCL) for dispatch of emergency services by calling the VCL Warm Transfer number: [contact] (DO NOT provide this number to Veterans).*
- *Provide Veteran information for Veterans Crisis Line: name, current location, phone number, date of birth*

Interviewer Reads (for VCL warm hand-off): *I am concerned for your safety and would like to reach out to the Veterans Crisis Line on your behalf. There will*

be a brief silence, please hold on the line while I transfer you to someone who is qualified to help you.

Interviewer Reads (if Veteran refuses): *I'd like to encourage you to contact your doctor or mental health provider and to call the Crisis Line whenever you need to. Their number is [name]. Thank you for your time, and I wish you all the best with your continued treatment.*

Abbreviated Script

Step 1: Once the Veteran has agreed to speak with someone at the VCL, let them know that there will be a brief silence as you get a VCL representative on the line.

Step 2: Press “Flash”, “Flashlink” or “Conference” button depending on the type of phone you are using.

[Veteran will now be on hold]

Step 3: Dial the VCL direct line. [contact])

Step 4: Once the VCL representative is on the line, describe the situation and provide the Veteran’s contact information

Step 5: Press “Flash”, “Flashlink” or “Conference” to get the Veteran back on the line.

[At this point all three people will be present.]

Step 6: Let the Veteran know that you will be getting off the line and hang up.

Additional Notes

- Call VCL ahead of time as it takes a while to connect
- Connect to the direct line (1-800 #) only if a warm hand-off is wanted
- Email is great way to connect with the VCL if there is a disconnection or if the Veteran declined a warm hand-off
- Provide background information of the Veteran to the VLC including birthday, location, phone #
- Must send suicidality forms encrypted
- Give the Veteran the 1-800 # if they want to use it later
- If you hang up, the Veteran and the VCL are still connected (unless you have a cell phone)

U.S. Department
of Veterans Affairs

TRANSFERRING A CALL TO THE VETERANS CRISIS LINE (VCL)

1. Determine if the caller is in distress.

a. Remain calm and listen.

b. Ask the question: "Sometimes when people are (upset/angry/in pain/etc.) they think about suicide. Are you thinking about killing yourself or someone else?"

Signs of Distress:

- Emotional (crying, loud, yelling)
- Making concerning statements like:
 - My family would be better off if I wasn't here.
 - I can't go on like this.
 - No one can help me.

YES

Suicidal, homicidal, or in crisis

NO

NOT suicidal, homicidal, or in crisis

Route caller to
appropriate local
resources.

2. Assess if caller is at **Imminent risk** (has already hurt self/others or has immediate plan to harm self/others and has access to means).

- Notify your supervisor (or other staff) of the situation.
- Try to obtain Veteran's information (phone number, name, last four digits of Social Security number, location).
- Have supervisor (or other staff) immediately contact [contact] for safety check.
- Remain on the phone with caller until emergency personnel arrive.

3. If caller is **not** at imminent risk, collect information:

- Caller's phone number (caller ID or ask for their phone number)
- Veteran's name
- Veteran's Social Security number (or last four digits of the SSN)
- Veteran's current location

4. Transfer the call:

- Explain that you will conference a VCL staff member into the call.
- Call [name], Press 1.
- Complete a **warm transfer**: When the VCL responder answers, identify yourself and the office you are calling from. Explain what is going on and provide the information that you collected about the caller before bringing the caller on the line.
- Inform caller that you will hang up and he or she is in good hands with the VCL responder.
- Make sure the caller is on the call with the VCL responder before hanging up.
- Document the initial call and warm transfer to VCL in a CPRS administrative progress note or Report of Contact (VA Form 119), as required locally. Notify your supervisor, per facility procedure or protocol.

For more information about the Veterans Crisis Line, visit VeteransCrisisLine.net

For more information about VA's mental health resources, visit www.mentalhealth.va.gov

© 7/15 VHA

